# 5. OBJECTIVES AND OUTCOME MEASURES

	Objectives	Outcome measures
Primary objective	Identify host and pathogen related	Differentially expressed host genes (≥ 2-fold
	determinants of severity of	difference in expression levels) as assessed
	community acquired acute	by RNA transcriptome microarray in
	respiratory infections (ARI) in adults.	hospitalised and primary care managed
		cases of ARI, stratified by pathogen* and
		comorbidity**.
		*Influenza virus, Human Rhinovirus, Respiratory
		Syncytial Virus, Streptococcus pneumoniae ; **No
		cardiovascular disease, chronic metabolic disease
		(diabetes)
Secondary	Describe the aetiology, clinical	In both groups:
objectives	management and outcomes of adult	Prevalence of detection of putative
	patients with community acquired	pathogens in respiratory tract samples.
	ARI, in both primary care and	
 
Proportion of cases receiving
 

	hospital care, across Europe.	antibiotics, antivirals, antifungals and/or
		immunomodulators.
		28 day mortality
		Additional in group 1 (primary care):
		
 
Proportion of cases requiring
 

		hospitalisation
		Additional in group 2 (hospitalised patients):
		
 
Severity of illness at enrolment as
 

		assessed by Pneumonia Severity Index
		(PSI) and CURB-65
		Proportion of cases requiring during
		admission: supplemental oxygen; non-
		invasive or invasive mechanical
		ventilation; extra-corporeal life support.
		Duration of invasive mechanical
		ventilation and extra-corporeal life
		support, if applicable
		Proportion of cases requiring Intensive
		Care Unit (ICU)/High Care Unit (HCU)
		admission
		Hospital - and ICU/HCU length of stay
		In-nospital mortality
Tertiary Objectives	To develop and validate prognostic	This is an exploratory objective. Some
	and diagnostic algorithms.	measures that could be included in
		algorithms are classifier gene sets based on
		host gene expression profiles, pathogen
		profiles, demographics, co-morbidities, risk
		factors, and clinical parameters. The
		diagnostic/prognostic algorithms will be
		evaluated for their ability to correctly
		diagnose infecting pathogen and/or predict
		adverse outcome in ARI.

PREPARE | Multi-centre EuRopean study of MAjor Infectious Disease Syndromes

13

Objectives	Outcome measures
To gain understanding into pathophysiological mechanisms contributing towards development of severe disease.	This is an exploratory objective to increase pathophysiological insights by integrative (systems medicine) analyses of pathogen- and patient characteristics. Measures that will be included in these integrative analyses are host gene expression profiles, clinical data on disease progression/outcome, deep sequencing of pathogen genomes and microbiomes.

# 6. PARTICIPANT IDENTIFICATION

## 6.1 Study participants

Group 1: Adults attending primary care with a new episode of community acquired respiratory tract illness

Group 2: Adults admitted to hospital with a new episode of community acquired respiratory tract illness.

# 6.2 Inclusion criteria Group 1 – primary care patients

- 1) Age  $\geq$  18 years
- 2) Patient is self-attending to primary care (i.e. not a home visit)
- 3) Clinical suspicion of a new episode of acute respiratory tract infection
- 4) Onset of the following symptoms within the last 14 days:
  - i. Sudden onset of self-reported fever OR temperature of  $\geq$  38°C at presentation AND
  - ii. At least one respiratory symptom (cough, sore throat, runny or congested nose, dyspnoea)

AND

iii. At least one systemic symptom (headache, muscle ache, sweats or chills or tiredness).

# 6.3 Exclusion criteria Group 1 – primary care patients

- 1) Patient lacks capacity to provide informed consent
- 2) No informed consent is provided by patient
- 3) The attending primary care physician decided to send patient to the hospital for assessment and possible hospital admission
- 4) Patient has been previously enrolled in the MERMAIDS-ARI study

# 6.4 Inclusion criteria Group 2 – hospitalised patients

1) Age ≥ 18 y

- 2) Clinical suspicion of a new episode of acute respiratory tract infection
- 3) Patient is admitted to hospital
- 4) Primary reason for hospital admission is clinical suspicion of a new episode of ARI
- 5) Onset of the following symptoms within the last 14 days:
  - Sudden onset of self-reported fever OR temperature of ≥ 38°C at presentation AND
  - ii. At least one respiratory symptom (cough, sore throat, runny or congested nose, dyspnoea)

AND

iii. At least one systemic symptom (headache, muscle ache, sweats or chills or tiredness).

## 6.5 Exclusion criteria Group 2 – hospitalised patients

- 1) Patient lacks capacity to provide informed consent
- 2) No informed consent is provided by patient
- 3) Patient has been transferred from another hospital
- 4) Patient has been previously enrolled in the MERMAIDS-ARI study

# 7. STUDY PROCEDURES

#### 7.1 Screening and eligibility assessment

Potential patients for the study will be identified by local PREPARE co-ordinators, clinicians, nurses, microbiologists or virologists and assessed against the eligibility criteria listed above and their eligibility recorded in the site study protocol. A 'Screening Log' will be maintained of all the patients who undergo screening regardless of whether they decide to participate in the study. If there is a delay between introduction of the study/initial eligibility assessment and consent, then the recruiter must confirm all eligibility criteria are still met.

# 7.2 Recruitment and informed consent

The participant must sign and date the latest approved version of the Informed Consent form before any study specific procedures are performed.

Written and verbal versions of the Participant Information Sheet and Informed Consent will detail the exact nature of the study; the implications and constraints of the protocol; and any risks involved in taking part. It will be clearly stated that the participant is free to withdraw from the study at any time for any reason without prejudice to future care, and with no obligation to give the reason for withdrawal. Participant Information Sheets will be available in the common local language.

Written Informed Consent will be confirmed by the dated signatures of the participant and by the person who presented and obtained the informed consent. The person obtaining consent must be suitably qualified and experienced, and be authorised to do so by the Principal Investigator. A copy of the signed Informed Consent will be given to the participants. The original signed form will be retained at the study site.

PREPARE | Multi-centre EuRopean study of MAjor Infectious Disease Syndromes

#### 7.2.1 Primary care

Participants will be identified by practice staff as they present naturally to primary care with an acute respiratory infection. Alternatively, advertisements may be used to invite potentially eligible participants to contact a recruiting primary care site to enquire about joining the study. In the primary care practice, a GCP-trained doctor or research nurse will assess the participants' eligibility and explain the study verbally to potential participants. They will also be given a Participant Information Sheet and allowed ample time to read it and ask questions. Consent will be taken by a GCP-trained doctor or research nurse.

#### 7.2.2 Secondary care

Potential participants may be identified by a member of their immediate care team and asked to give a verbal consent to be approached by research staff who are not members of their care team. If they agree to this then the verbal consent will be recorded in the participant's medical record. Written and verbal versions of the Participant Information Sheet and Informed Consent will then be presented by GCP-trained study staff. Consent will be taken by a GCP-trained doctor or research nurse.

#### 7.2.2.1 Study consenting procedures during the SARS-CoV-2 pandemic

During the SARS-CoV-2 / COVID-19 pandemic, study procedures are adjusted to minimalize interference with clinical care and reduce the burden on the patient, especially with regard to shortages of personal protection materials. The following adjustments will be applied:

Patients who are eligible for the study will be approached by a member of their healthcare team. Verbal information on the study will be provided. If the patient gives verbal informed consent to participate in the study, the study procedures will be executed. Verbal informed consent will be recorded in the patient notes. Once the patient is deemed non-infectious, a member of the healthcare team will undertake the informed consent procedure as stated in section 7.2.2.

# 7.3 Withdrawal from study

Patients are free to withdraw consent at any time without providing a reason. Patients who wish to withdraw consent for the study will have anonymised data collected up to the point of that withdrawal of consent included in the analyses. The patient will not contribute further data to the study. Data up to the time of withdrawal will be included in the analyses unless the patient explicitly states that this is not their wish.

# 7.4 Co-enrolment

Subjects may be co-enrolled in other studies if the study co-ordinators have been informed and have given their approval, to ensure the other study would not interfere with the results of this study or compromise patient welfare.

# 7.5 Potential risks and benefits

Since this is an observational study, we do not foresee any risks involved in participating in the study, and during the informed consent process the opportunity will be given to understand the objectives and any inconveniences of the study. Participating in the study will not directly benefit the participant, but will provide information on the burden, aetiology, risk factors, medical management and outcomes of the diseases and inform prevention, management and future research and management of emerging or (re-)emerging infections with epidemic potential.

## 7.6 Baseline assessments and subsequent visits

Following provision of consent, baseline data will be collected from patient medical charts and/or patient interview. Biological samples and information on treatment and care from subjects attending primary care (group 1) will be collected according to the schedule in Table 1a. They will have clinical baseline data and samples taken on day 0 and be invited for a follow up appointment on day 2 for sampling.

For subjects admitted to hospital (group 2), samples and data will be collected according to Table 1b.

Patients in both groups will be followed up at discharge and on day 28 for mortality. In order to avoid loss to follow up, in exceptional circumstances where a participant may not be able to attend hospital or their GP surgery/outpatient clinic, the day 28 follow up visit may take place in the participant's home or their place of work.

Davi	0	н	2	2 8⁺
Day				
Eligibility screen	Х			
Informed consent	Х			
Baseline data	Х			
Nasopharyngeal Swab	Х			Х
Nasopharyngeal RNA	Х			Х
Physical examination	Х			
EDTA blood	Х		Х	
RNA blood	Х		Х	Х
SST blood (serum)	Х			Х
Patient symptom scores	Х			Х
Concomitant meds		Х	Х	Х
Follow up of outcomes				Х

#### Table 1a. Schedule of procedures for subjects included in group 1 (primary care)

Day 0 = at initial presentation

Day 2 = 2 days after initial presentation. Delay of Day 2 blood sample collection up to Day 4 will be permissible. + = -3/+21days

Table 1b. Schedule of procedures for subjects included in group 2 (hospital admissions)

Day	0	τ	2	3 to discharge	At discharge^	28 †
Eligibility screen	Х					
Informed consent	Х					
Baseline data	Х					
Nasopharyngeal Swab	Х				Х	Х
Nasopharyngeal RNA	Х				Х	Х
Tracheal aspirate#	-	-	-	-		
Bronchoalveolar lavage fluid (BALF)#	-	-	-	-		
Physical examination	Х					
EDTA blood	Х		Х		Х	
RNA blood	Х		Х		Х	Х
SST blood (serum)	Х					Х
Clinical observations	Х	Х	Х	Х	Х	Х
Concomitant meds		Х	Х	Х	Х	Х
Clinical management		Х	Х	Х	Х	
Follow up for outcome						Х

Day 0 = within 24h of hospital admission

Day 2 = 2 days after hospital admission. Delay of Day 2 blood sample collection up to Day 4 will be permissible. # = if available at any time from clinical diagnostic procedure

^if discharged before or on day 2, then discharge samples will replace the day 2 samples  $\pm -3/+21$  days

# 7.7 Clinical parameters

#### 7.7.1 From all subjects

- Patient demographics and medical history, at enrolment
- Description of clinical signs and symptoms, in the 14 days before enrolment and at enrolment (Day 0)
- Physical examination, at enrolment (including respiratory rate and oximetry see CRF for complete list)
- Discharge/final diagnosis as determined by attending physician
- Presence of febrile illness at day 28
- Mortality at day 28

#### 7.7.2 Additional clinical parameters from Group 1

- in the 14 days before enrolment to day 28:
  - All relevant laboratory results as ordered by routine care
  - All relevant prescribed medication (e.g. antivirals, antibiotics, antifungals, antiinflammatory drugs, steroids, other immune modulators, statins, ACEinhibitors/angiotensin receptor blockers).
  - Results of all relevant microbiological testing as ordered for routine care

- Percentage of patients admitted to hospital by day 28

#### 7.7.3 Additional clinical parameters from Group 2

- Pneumonia Severity Index (PSI) at admission
- CURB-65 severity score, at enrolment
- Requirement of (at any time during admission):
  - supplemental oxygen
  - non-invasive mechanical ventilation
  - invasive mechanical ventilation
  - extra-corporeal life support
- If applicable, duration of invasive mechanical ventilation and extra-corporeal life support
- In the 14 days before admission to day 28:
  - All relevant laboratory results as ordered by routine care
  - All relevant prescribed medication (e.g. antivirals, antibiotics, antifungals, antiinflammatory drugs, steroids, other immune modulators, statins, ACEinhibitors/angiotensin receptor blockers).
  - Results of all relevant microbiological testing as ordered for routine care
- Date of hospital admission and discharge, transfer or death
- Date of high care unit/intensive care unit admission and discharge, transfer or death, if applicable
- Clinical outcome: hospital discharge, transfer or in-hospital death

# 7.8 Definition of co-morbid phenotypes

#### A. Chronic pulmonary disease

#### Definition:

- Patients with confirmed COPD (chronic bronchitis or emphysema) OR possible COPD diagnosed by a Physician or the study team from data recorded in the clinical notes
- Patients diagnosed with asthma by a Physician and on regular (or seasonal) treatment with inhaled corticosteroids
- Patients with a diagnosis of Cystic Fibrosis or other bronchiectasis conditions
- Patients on regular medical or supportive (O2) treatment for non-infectious Interstitial lung disease (e.g. pulmonary fibrosis, asbestosis, autoimmune)
- Patients with neuromuscular pulmonary disease (e.g. Amyotrophic Lateral Sclerosis, Muscular Dystrophy, Myasthenia Gravis)

#### **B.** Chronic cardiovascular disease

Patients diagnosed by a physician AND on regular medication or with pacemaker/VAD for any of the below:

<sup>1 WHO http://www.euro.who.int/en/health-topics/noncommunicable-diseases/cardiovascular-diseases/card

PREPARE | Multi-centre EuRopean study of MAjor Infectious Disease Syndromes

- Coronary Artery Disease (e.g. Angina, Chronic Heart Disease, ischaemic or atherosclerotic heart disease)
- Chronic / congestive heart failure
- Cerebrovascular disease (ischaemic or haemorrhagic stroke, or transient ischaemic attack)
- Congenital heart disease
- Cardiomyopathy

#### C. Metabolic disease - diabetes

Patients diagnosed with Type 1 or Type 2 diabetes by a Physician or Nurse specialist AND requiring daily insulin or oral diabetes medication to control their diabetes.

#### 7.9 Laboratory assessments

Laboratory samples to be analysed by the reference laboratories in Antwerp and Amsterdam, as described in Table 2. Laboratory samples will be labelled with a unique code allocated to each patient at enrolment. No patient identifiable information will be shared with the reference laboratory. Results will be reported back to study sites at the end of the study.

Specimen	Collection container	Assay	Archive sample in biobank	Centralised/ Decentralised testing
Flocked	UTM Viral	Identification and	Yes	Centralised
Nasopharyngeal	Transport	quantification of putative		
swab	Media	respiratory pathogens		
Nasopharyngeal	RNA conserving	Microarray analysis of host	Yes	Centralised
RNA	NP swab kit	transcriptome		
Blood	EDTA	Innate and adaptive	Yes	Centralised
	vacutainer	immune markers		
Blood	Tempus™ Blood	Microarray analysis of host	Yes	Centralised
	RNA tube	transcriptome		
Blood	Serum-	Soluble inflammatory	Yes	Centralised
	separating	mediators and serum bank		
	vacutainer	(PREPARE Task 3.2)		
Tracheal aspirate/	Sterile	Pathogen identification,	Yes	Centralised
BALF#	container	pathogen shedding		

#### Table 2: Laboratory assessments, ARI observational study

# = if available from routine clinical diagnostics

#### 7.10 Sample handling

Sample handling will adhere to the PREPARE Multi-centre EuRopean study of MAjor Infectious Disease Syndromes (MERMAIDS) guidelines for sample handling.

#### 7.11 Standard of care for sampling from patients

Samples taken for the purpose of medical management will, at all times, have priority over samples requested for research reasons. Research samples will, wherever possible, be collected at a time coinciding with samples taken for routine care.

PREPARE | Multi-centre EuRopean study of MAjor Infectious Disease Syndromes

# 7.12 Future use of samples

Samples collected will be used for the purpose of this study as stated in the protocol and stored for future analyses that are relevant to the study questions. The standard consent form will request consent from subjects for sample storage and/or export of samples to collaborating institutions for investigations that cannot be performed locally. Any proposed plans to use samples other than for those relevant to the study question will be submitted to the relevant ethics committees prior to any testing.

Any database will only identify participants by a participant number. Participant names or any other identifying details will NOT be included in the central database. Data may be used alone or in combination with data from related studies in secondary analyses.

#### 7.13 Medical management and safety reporting

Medical management will be according to standard of care at the treating site and not a part of this research protocol. The research only includes collection of clinical information and specimens and therefore adverse event reporting is not applicable as there is no intervention.

## 7.14 Discontinuation/withdrawal of participants from study

Subjects can leave the study at any time for any or no reason if they wish to do so without any consequences. The investigator can decide to withdraw a subject from the study for urgent medical reasons.

## 7.15 Definition of end of study

The end of the study will be the date when all enrolled patients have completed their 28 day follow up.

# 8. STATISTICS AND ANALYSES

#### 8.1 Statistical considerations regarding power calculation

#### 8.1.1 General approach to power calculation

The primary aim of this study is to detect differentially expressed genes as assessed by RNA transcriptome, across all groups of major pathogens and major comorbidity groups. To determine the total number of subjects required to answer this question, these groups are firstly defined (8.1.2). Then the minimally required group size necessary to detect differentially expressed genes between two groups is determined (8.2). Based on the estimated prevalence of the pathogens and comorbidities, the power calculation is performed to determine the minimal amount of subjects in group 2 (8.3.1) and group 1 (8.3.2).

#### 8.1.2 Subgroup comparisons

We have performed sample size calculation on the ability to detect differentially expressed genes with a statistical power of at least 90% between all groups across the major pathogens (influenza virus, human rhinovirus, respiratory syncytial virus and *Streptococcus pneumoniae*), and major comorbidity groups (no comorbidity, chronic pulmonary disease, chronic cardiovascular disease, and chronic metabolic disease in hospitalised patients, and between primary care patients without comorbidities (Figure 1). Basing our power calculation on these subgroups will subsequently provide enough statistical power to detect differentially expressed genes in a number of other aetiologies across these comorbidities as well as for our secondary study objectives.

PREPARE | Multi-centre EuRopean study of MAjor Infectious Disease Syndromes

#### Figure 1. Predefined relevant subgroups for power calculation

**A.** This figure represents the predefined subgroups for each ARI aetiology (viruses and bacteria). The sample size estimation is based on achieving a statistical power of >90% for detection of differentially expressed genes in predefined subgroups (e.g. Influenza, HRV, RSV, *Streptococcus pneumoniae*). The statistical power to detect differentially expressed genes in other comorbidities in the above mentioned pathogens will vary (e.g. cancer/ immunosuppressive condition/obesity approx. 80-90%). **B.** This figure displays the subgroups in which we will analyse the differences and commonalities in the transcriptional profiles of hospitalised patients with a specific comorbidity across the different pathogens. The statistical power to investigate these comorbidities in other pathogens will vary (e.g. Parainfluenza virus >90% in chronic pulmonary disease and no comorbidity, coronaviruses approx. 50-80%).

# 8.2 Estimation of minimally required group sizes

We assume that the expression of each gene is normally distributed on the log scale and that the variance is the same in the different groups and thus the only difference between the groups is the mean. At an alpha of 0.05 and at an expected standard deviation of the gene intensity measurements on the base-two logarithmic scale of 0.7 (realistic for genes that are expressed at moderate to high levels), we expect to be able to detect 90% of >2 fold differentially expressed genes (i.e. an absolute effect size of 1 on a base-two logarithmic scale) between groups of 11 patients. These estimations are likely to be on the conservative side as we chose to err on the side of caution with regard to the chosen value for standard deviation. The calculation was based on the Affymetrix HG U133plus2 microarray platform, which contains 54,515 probe-sets.

	effect size in fold change			
power	2	1.75	1.5	
60%	5	8	15	
70%	7	10	18	
80%	8	12	23	
90%	11	16	31	
95%	13	20	38	

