# 8.4 Statistical considerations regarding outcome measures

#### 8.4.1 RNA expression profiles

#### Correction for Multiple Comparisons

To control for multiple testing and reduce the false positive rate (FDR), stringent statistical criteria will be used to identify nominal 2-fold differentially expressed genes (i.e. effect size of 1 in absolute terms on a base-two logarithmic scale) with raw P-value < 0.05 and Benjamini-Hochberg False Discovery Rate <0,05.

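### The 90% power claimed for 11 patients per group is calculated at an unadjusted alpha of 0.05 and does not hold under the protocol's own false discovery rate rule

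*Protocol*

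**What the plan says.** Section 8.2 assumes log-scale normality and equal variances. It works "At an alpha of 0.05 and at an expected standard deviation of the gene intensity measurements on the base-two logarithmic scale of 0.7", takes "an absolute effect size of 1 on a base-two logarithmic scale" as the difference to detect, and concludes: "we expect to be able to detect 90% of >2 fold differentially expressed genes" "between groups of 11 patients". It names a microarray platform with 54,515 probe-sets, and it calls its estimates probably conservative because of the SD chosen. Table 3 gives group sizes for five power levels and three fold changes.

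Section 8.4.1 (Correction for Multiple Comparisons) sets the rule for calling a gene: a nominal 2-fold difference "with raw P-value < 0.05 and Benjamini-Hochberg False Discovery Rate <0,05". Section 3.4.1 gives the same rule.

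The group size of 11 then carries the sample size. Section 8.1.2 says the calculation was done "with a statistical power of at least 90% between all groups across the major pathogens" and comorbidity groups, and the legend of Figure 1 repeats a figure above 90%. Section 8.3 finds that 1,500 hospitalised and 500 primary care patients give at least 11 in every required cell. The synopsis plans more: 2,250 and 750.

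**The concern.** The stated power belongs to one decision rule and the analysis uses another. With tens of thousands of probe-sets, a gene usually needs a raw p-value far below 0.05 to pass a 5% FDR, so a calculation at 0.05 overstates the share of true 2-fold genes that will be called. The number of probe-sets is mentioned in section 8.2 but does not enter the result.

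The statement concerns the primary objective and is the only basis given for the sample size. A reader who relies on 90% detection could give a short gene list from a small pathogen-comorbidity cell more weight as evidence of no difference than it deserves.

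**Working it through.** **1. Reproducing Table 3.** Inputs from section 8.2: SD 0.7 in both groups, alpha 0.05, difference log2(fold change). Sidedness is not stated; two-sided reproduces the table. The formula is n = 2 × 0.7² × (1.96 + z_power)² / log2(FC)².

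For 2-fold and 90%: 2 × 0.49 × (1.96 + 1.2816)² / 1² = 10.30, rounded up to 11.

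| Fold change | 60% | 70% | 80% | 90% | 95% |
|---|---|---|---|---|---|
| 2 | 4.80 → 5 | 6.05 → 7 | 7.69 → 8 | 10.30 → 11 | 12.73 → 13 |
| 1.75 | 7.37 → 8 | 9.28 → 10 | 11.80 → 12 | 15.80 → 16 | 19.54 → 20 |
| 1.5 | 14.03 → 15 | 17.68 → 18 | 22.48 → 23 | 30.09 → 31 | 37.22 → 38 |

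All 15 match, so no multiplicity adjustment entered. A one-sided test would give 9 for 2-fold and 90%. The exact t-test gives 12, with 89.0% power at 11.

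**2. Power at n = 11 under the FDR rule.** Let π be the share of probe-sets that are truly 2-fold, the rest being null. The effective raw threshold t solves t = 0.05 × [(1 − π) × t + π × power(t)]. The protocol gives neither π nor the per-gene test, so both are varied.

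| π (assumed) | t-test: threshold | t-test: power | Normal: threshold | Normal: power |
|---|---|---|---|---|
| 1% | 0.00004 | 8% | 0.00018 | 35% |
| 5% | 0.0009 | 33% | 0.0015 | 57% |
| 10% | 0.0025 | 48% | 0.0035 | 67% |
| 20% | 0.0065 | 63% | 0.0079 | 76% |
| 50% | 0.020 | 79% | 0.022 | 86% |

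Simulating Benjamini-Hochberg on 54,515 independent probe-sets with the t-test gave 8.8%, 33.6% and 48.0% at 1%, 5% and 10%. For 90% power at those shares, n per group is 26 / 21 / 19 (t-test) or 23 / 19 / 17 (normal).

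**3. The 2-fold criterion.** If it applies to the observed change, a gene whose true change is exactly 2-fold passes it about half the time, because its estimate is centred on the cut-off. Adding this filter to the simulation at n = 11 gave 8.7%, 31.1% and 41.1% at 1%, 5% and 10%, and 47.6% at 20%. Power for such a gene is then capped near 50% at any group size.

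**4. Planned cell sizes.** These use the mean prevalences of Tables 4 and 5 and assume that pathogen and comorbidity are independent. The smallest hospital cell is rhinovirus with cardiovascular disease: 1,500 × 0.039 × 0.209 = 12.2, and 2,250 × 0.039 × 0.209 = 18.3. FDR-only power for 18 against 18 is 61% / 82% / 88% (t-test) or 77% / 89% / 93% (normal) at 1% / 5% / 10%. For 18 against 31 (rhinovirus without comorbidity, 2,250 × 0.039 × 0.358 = 31.4), t-test power is 84% / 94% / 96%.

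**The case against.** A reader might infer that power at 11 per group simply is 8% to 48%. The protocol does not support that as a flat statement. It names no per-gene test and gives no share of changed genes, and the approximation it used gives 35% to 67% for the same shares. The model is also stark, with every changed gene at exactly 2-fold and all others null. Section 8.2 speaks of changes above 2-fold, and larger or additional real effects would relax the FDR threshold. The low end is therefore fragile.

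A reader might also infer that the study is underpowered throughout, or needs more patients. That does not follow either. The planned totals are 1.5 times those in section 8.3. At mean prevalences, 15 of the 16 hospital cells reach 19 and 10 of 16 reach 26, and many comparisons set a small cell against a larger one. Cells would be smaller at the low ends of the prevalence ranges.

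A third inference, that an SD of 0.7 is not cautious, has nothing in the document behind it. With an SD of 0.5 (my assumption), t-test power at 11 per group would be 64% / 86% / 92% at 1% / 5% / 10%. But section 8.2 does not offer the SD margin as payment for multiplicity.

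These points narrow the size of the problem. They do not reconcile an alpha of 0.05 with an FDR rule. Nor is this detail left to a statistical analysis plan, since the protocol states both the power and the rule that contradicts it.

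**Conclusion.** The mismatch is certain and needs no outside figure: Table 3 is an unadjusted single-gene calculation, and the analysis calls genes at a 5% FDR. At SD 0.7, power for a true 2-fold gene with 11 per group stayed below 90% under both tests at every share tried, up to 50%. How far below depends on the assumed share, the test and independence of probe-sets.

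At the planned size the shortfall lies mainly in pairs of small cells and at low shares of changed genes. That conclusion covers the FDR part only; if the 2-fold criterion applies to the observed change, step 3 limits power further. FDR control in the analysis is unaffected. What is wrong is the power justification.

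**What to change.** Keep enrolment as planned and correct the text:

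- Replace Table 3 and the wording of section 8.2 with power at the FDR threshold. State the per-gene test and a range for the share of changed genes, for example 1%, 5% and 10%.
- Say in sections 3.4.1 and 8.4.1 whether the 2-fold criterion applies to the observed change. If it does, include it in the power calculation, or state power for a true change larger than 2-fold.
- Restate the 90% claims in sections 8.1.2 and 8.3 and in Figure 1 as power, or as detectable fold change, at the cell sizes expected from 2,250 and 750.
- Limit the remark about conservative estimates to the choice of SD.

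The cost is wording and a recalculation, and the stated power becomes less favourable.
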